7.2 Medical History

Medical and Surgical History: A complete medical and surgical history (which includes CD-onset date), history of tobacco and alcohol use, will be obtained from each subject during the Screening Period. An updated medical history will be obtained at the Baseline (Week 0) Visit to ensure that the subject still qualifies. Medical history will be summarized using body system and condition/diagnosis for ITT analysis by treatment group. No statistical tests will be performed.

Chest X-Ray Results: All subjects undergo a standard chest x-ray (including a posteroanterior [PA] and lateral view) or chest CT during the Screening Period. Number and percent of subjects with presence or absence of finding for the previous TB infection, calcified granulomas, pleural scarring/thickening, and other findings will be presented by treatment group. No statistical tests will be performed.

TB Test Results: QuantiFERON TB Gold test at Screening Visit will be summarized. QuantiFERON-TB tests will be described as positive, negative or indeterminate. No statistical tests will be performed.

TB Prophylaxis: History of use of TB prophylaxis or initiation of TB prophylaxis will be summarized.

ECG Results: ECG results at Screening will be presented as frequency distribution showing results as Normal, Abnormal (Not clinically significant), Abnormal (Clinically significant) and Unable to evaluate/missing. No statistical tests will be performed.

7.3**Previous Treatment and Concomitant Medications**

The previous and concomitant medications are defined in the protocol. Based on generic medication names, these categories of medications used by subjects before and during the study will be summarized by number and percent for ITT analysis set for the treatment groups. No statistical tests will be performed.

The number and percent of subjects using Crohn's disease specific medications including corticosteroids, aminosalicylates, immunomodulators (azathioprine, mercaptopurine, methotrexate, or other), and antibiotics within 90 days prior to Baseline, and at Baseline will be tabulated. The number and percentage of subjects using CD-specific immunomodulators at any time prior to Baseline will also be tabulated.

8.0**Patient Disposition**

Subject disposition will be presented for subjects in the ITT analysis set using the following information by treatment group:

- Number and percent of subjects by treatment group and by investigator and/or site number in DB and OL periods
- Number and percent of subjects completing the DB Week 0 – 4, Week 0 – 8 and OL Week 8 – 26, and discontinuing during the DB Week 0 – 4, Week 0 – 8 and OL Week 8 – 26 visits, respectively
- Subject disposition, including the number and percent of subjects who prematurely discontinued during the DB Week 0 – 4, 0 – 8, and OL Week 8 – 26, respectively, by primary reason and by any reason

Summary of protocol deviations will be provided.

9.0**Study Drug Exposure and Compliance**

Study drug exposure and compliance will be summarized using the mean, standard deviation, minimum, median, and maximum. Exposure to study drug (total patient years) will be summarized for each treatment group using Safety Analysis Set.

- Total exposure for DB placebo controlled period = date of Week 4 injection – date of first study drug dose, for subjects who did not prematurely discontinue before Week 4; If a subject discontinued at or before Week 4, then exposure is defined as "date of last injection prior to Week 4 – date of first injection + 14 days or the date subjects initiate adalimumab therapy not supplied in the context of Study M14-233, whichever comes first."

The number of injections received at each schedule time point will be summarized with number and percent for each treatment group using Safety Analysis Set.

Compliance (%) is defined as the number of injections received divided by the number of injections planned (rounded to 0.1) during the subject's participation in Study M14-233 and multiplied by 100 (rounded to 0.1%). Treatment Compliance will be summarized for the safety analysis set using descriptive statistics. Subjects with missing data for the number of injections returned will be excluded from the summary.

10.0 Efficacy Analysis

10.1 General Considerations

All statistical tests will be two-sided with the significance level of 0.05. Descriptive statistics will be provided. These include the number of observations, mean, standard deviation, minimum, median, and maximum for continuous variables; and number and percent for discrete variables. The analysis will be performed using SAS® (SAS Institute Inc., Cary, NC, USA).

10.2 Primary Efficacy Analyses

This section provides the details of the primary efficacy analysis for the study.

Primary Efficacy Variables:

Proportion of subjects who achieve clinical remission (CDAI < 150) at Week 4.

Analysis Data Set for the Primary Efficacy Analysis:

The primary efficacy analysis will use the ITT analysis data set.

Imputation Method Used for the Primary Efficacy Analysis:

The primary efficacy analysis will use the NRI method to impute the missing values at Week 4. Subjects with missing primary endpoint data at Week 4 will be classified as "no clinical remission."

Statistical Method of the Primary Efficacy Analysis:

The comparison for the difference between the treatment groups on the primary efficacy variable will be performed using the Cochran-Mantel-Haenszel (CMH) test and will be stratified by Crohn's disease severity (CDAI ≤ 300 , > 300) at Baseline and corticosteroid use at Baseline. A CMH based two-sided 95% confidence interval for the difference between the treatment groups will be calculated. Missing CDAI will be imputed using the non-responder imputation (NRI) approach. Subjects who dose escalate will be imputed using NRI for visits after dose escalation. The last observation carried forward (LOCF) method will also be used as the sensitivity analyses.

10.3 Secondary Efficacy Analyses

The Week 26 efficacy endpoint is proportion of subjects who achieve clinical remission at Week 26 (CDAI < 150) in subjects who achieved clinical response (decrease in CDAI ≥ 70 points from Baseline) at Week 8. The one sample Exact test will be performed by comparing it to the clinically meaningful remission rate of 30%, and the two-sided 95% CI will be provided.

Key secondary efficacy endpoints include:

- Proportion of subjects who achieve CDAI < 150 plus a reduction in hs-CRP of at least 50% from Baseline at Week 4.
- Proportion of subjects who achieve CDAI < 150 plus a reduction in hs-CRP of at least 50% from Baseline at Week 26 in subjects who achieved decrease in

CDAI \geq 70 points from Baseline plus at least 30% reduction in hs-CRP from Baseline at Week 8.

- Proportion of subjects who discontinue corticosteroid use and achieve clinical remission (CDAI $<$ 150) at Week 26 in subjects who were taking steroids at Baseline and who achieved clinical response (decrease in CDAI \geq 70 points from Baseline) at Week 8.
- Proportion of subjects who discontinue corticosteroid use and achieve CDAI $<$ 150 plus a reduction in hs-CRP of at least 50% from Baseline at Week 26 in subjects who were taking steroids at Baseline and who achieved decrease in CDAI \geq 70 points from Baseline plus a reduction in hs-CRP of at least 30% from Baseline at Week 8.
- Proportion of subjects who achieve clinical response (decrease in CDAI \geq 70 points from Baseline) at Week 4.
- Proportion of subjects who achieve decrease in CDAI \geq 70 points from Baseline plus a reduction in hs-CRP of at least 30% from Baseline at Week 4.
- Proportion of subjects who achieve CDAI $<$ 150 and hs-CRP $<$ 3 mg/L at Week 4.
- Proportion of subjects who achieve CDAI $<$ 150, hs-CRP $<$ 3 mg/L at Week 26 in subjects who achieved clinical response (decrease in CDAI \geq 70 points from Baseline) at Week 8.
- Proportion of subjects who achieve IBDQ remission (IBDQ \geq 170 points) at Week 4.
- Proportion of subjects who achieve IBDQ remission at Week 26 in subjects with clinical response (decrease in CDAI \geq 70 points from Baseline) at Week 8.
- Change from Baseline in fecal calprotectin level at Week 4.
- Proportion of subjects who achieve CDAI $<$ 150, hs-CRP $<$ 3 mg/L and fecal calprotectin $<$ 250 μ g/g at Week 4.
- Proportion of subjects who achieve CDAI $<$ 150, hs-CRP $<$ 3 mg/L and fecal calprotectin $<$ 250 μ g/g at Week 26 in subjects who achieved clinical response (decrease in CDAI \geq 70 points from Baseline) at Week 8.

Additional secondary endpoints include:

- Proportion of subjects with clinical remission (CDAI < 150) over time.
- Proportion of subjects with CDAI < 150 plus a reduction in hs-CRP of at least 50% from Baseline over time.
- Proportion of subjects with clinical response (decrease in CDAI \geq 70 points from Baseline) over time.
- Proportion of subjects with decrease in CDAI \geq 70 points from Baseline plus a reduction in hs-CRP of at least 30% from Baseline over time.
- Change from Baseline in CDAI over time.
- Change from Baseline in hs-CRP level over time.
- Change from Baseline in fecal calprotectin level over time.

The analysis over time will be performed for the DB placebo-controlled period (Week 0 to Week 4), with comparisons between active treatment and placebo groups. The analysis over time will also be performed for Any Adalimumab set (the entire study on or after the first dose of adalimumab), with only summary statistics for adalimumab treatment.

Exploratory endpoints include:

- Proportions of subjects who achieve CDAI < 150 at Week 26 in subjects who did not achieve clinical response (decrease in CDAI \geq 70 points from Baseline) at Week 8.

For categorical endpoints with comparison between the treatment groups, the difference in proportions of subjects between treatment groups will be analyzed using the CMH test adjusted for stratification variables. Additionally, the CMH based two-sided 95% confidence interval for the difference in proportions will be provided. For categorical endpoints with comparison to the clinically meaningful constant rate, the one sample Exact test will be performed and the two-sided 95% CI will be provided. The NRI imputation method will be used for subjects with missing data at the time point

evaluated. Subjects who dose-escalate will be imputed using NRI for visits after dose escalation. The LOCF method will also be used as the sensitivity analyses.

Change from Baseline in continuous endpoints will be analyzed using Analysis of Covariance (ANCOVA) model including factor for treatment group, stratification factors and Baseline values. For analyses of changes from Baseline variables, both LOCF and observed case analyses will be performed. The LOCF analysis is considered primary for inferential purposes.

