4.2 Design Diagram

This is a Phase 3, randomized, double-blind, placebo controlled, multicenter study of adalimumab in anti-TNF naïve Chinese subjects with moderately to severely active CD ($220 \leq \text{CDAI} \leq 450$) and elevated hs-CRP ($\geq 3 \text{ mg/L}$). The study consists of an 8-week DB period followed by an OL period of 18 weeks. Subjects will be randomized in a 1:1 ratio to receive adalimumab or placebo at Baseline. Subjects randomized to adalimumab at Week 0 will receive blinded adalimumab 160 mg at Week 0, 80 mg at Week 2, and 40 mg at Week 4 and Week 6. Subjects randomized to placebo at Week 0 will receive blinded placebo at Week 0 and Week 2, then will receive blinded adalimumab 160 mg at Week 4 and 80 mg at Week 6. At Week 8, all subjects will enroll in an 18-week OL period to receive adalimumab 40 mg every other week (eow). No drug will be administered at the final study visit.

The study was designed to enroll approximately 200 subjects to meet scientific and regulatory objectives without enrolling an undue number of subjects in alignment with ethical considerations.

[figure not shown]
The study duration will be up to 39 weeks, and will include a screening period of up to 35 days, an 8-week double blind treatment period, an 18-week OL period and a 70-day follow-up period. All subjects will have a follow-up phone call approximately 70 days after the last administration of study drug to obtain information on any new or ongoing AEs. The 70-day follow-up phone call will not be required for any subject who initiates adalimumab therapy not supplied in the context of Study M14-233 after the end of study participation.

At or after Week 12, any subject who experiences inadequate response may increase dose to OL adalimumab 80 mg eow. If the subject has received OL 80 mg eow therapy and continues to demonstrate inadequate response, he or she should be withdrawn from the study per PI discretion.

Subjects may discontinue adalimumab treatment at any time during study participation. Subjects who end study participation early will have a Premature Discontinuation Visit.

A schematic of the study design is shown in [Figure 1](#).

Figure 1. Study Design

The study activities are presented in [Table 1](#).

Table 1. Study Activities

Activity	Screening (35 Days)	Day -21 ^a	Day -7 ^a	Baseline (Wk 0) ^b	Wk 2	Wk 4	Wk 6	Wk 8	Wk 10	Wk 12	Wk 14	Wk 16	Wk 18	Wk 20	Wk 22	Wk 24	Wk 26/ Premature Discontinuation	Unscheduled Visit	70-Day Follow-Up Call ^c

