5.0 Analysis Populations

5.1 Definition for Analysis Populations

The following populations will be used for analyses in this study:

Intent-to-Treat (ITT) set includes all subjects who are randomized. ITT subjects will be analyzed as randomized. ITT set is the primary population for the efficacy analysis during the DB and OL treatment periods.

The Safety set consists of all enrolled subjects who received at least one injection of study drug. The safety set will be analyzed as treated, according to treatment the subject actually received. The safety set will be used only for safety analysis.

The Any Adalimumab set consists of all enrolled subjects who received at least one injection of adalimumab.

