6.0 Analysis Conventions

Definition of Baseline

The Baseline Visit date is the date when the first dose of study drug is received and referred to as Day 1 or Week 0. The baseline value for a variable is defined as the last non-missing value on or before the date of the first dose of study drug.

When analyzing laboratory parameters and vital signs on the Any Adalimumab analysis set, the Baseline Visit date is the date when the first dose of adalimumab is received and will be counted as Day 1 or Week 0. The baseline value for a laboratory or vital sign measurement is defined as the last non-missing value on or before the date of the first dose of adalimumab.

Definition of Final Observation

Final observation in the 4-week DB placebo controlled treatment period is defined as the last non-missing observation collected within 70 days following the last dose of study drug or the date subjects initiate adalimumab therapy not supplied in the context of Study M14-233 for subjects who discontinue the study before Week 6, and on or before the day of the first dose of study drug at Week 6 for subjects who continues the study.

Final observation in the DB/OL period for the Any Adalimumab set is defined as the last non-missing observation collected within 70 days following the last dose of study drug, or the date subjects initiate adalimumab therapy not supplied in the context of Study M14-233.

Definition of Rx Days (Days Relative to the First Dose of Study Drug)

Rx Days are calculated for each time point of interest and provide a quantitative measure of days between the event and Day 1 (which can be the day of the first dose of study drug or the day of the first dose of adalimumab, depending on the analysis). That is, the Rx Day is calculated as the event date minus Day 1 plus 1. The Rx Day will be a negative value when the time point of interest is prior to Day 1, and the Rx Day will be a positive

value when the time point of interest is after Day 1. By this calculation algorithm, the first dose day is Rx Day 1, while the day prior to the date of first dose is defined as Rx Day –1 (there is no Rx Day 0). Rx Days are used to map actual study visits to the protocol-specified study visits.

Definition of Analysis Windows

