Week 8 DB	57	51 – 71 ^b
Week 12 OL	85	72 ^c – 99
Week 16 OL	113	100 – 127
Week 20 OL	141	128 – 162
Week 26 OL	183	163 – 190

Rx Day A = date of visit – date of first study drug injection in double-blind treatment period + 1

- a. Date of first study drug injection in double-blind treatment period.
- b. For Week 8 DB, visit window was from Rx Day 51 to Rx Day 71 or the date of the first injection in OL period (if applicable), whichever comes first.
- c. For Week 12 OL, visit window was from Rx Day 72 or the date of the first injection in OL period + 1 (if applicable), whichever comes first, to Rx Day 99.

Table 4. Visit Windows for Analysis of Urinalysis

Scheduled Week	Nominal Day	Time Window (Rx Day A Range)
Week 0 DB	1 ^a	≤ 1
Week 4 DB	29	2 – 43
Week 8 DB	57	44 – 71 ^b
Week 12 OL	85	72 ^c – 112
Week 20 OL	141	113 – 161
Week 26 OL	183	162 – 190

Rx Day A = date of visit – date of first study drug injection in double-blind treatment period + 1

- a. Date of first study drug injection in double-blind treatment period.
- b. For Week 8 DB, visit window was from Rx Day 37 to Rx Day 71 or the date of the first injection in OL period (if applicable), whichever comes first.
- c. For Week 12 OL, visit window was from Rx Day 72 or the date of the first injection in OL period + 1 (if applicable), whichever comes first, to Rx Day 112.

Table 5. Visit Windows for Analysis of Fecal Calprotectin and IBDQ

Scheduled Week	Nominal Day	Time Window (Rx Day A Range)
Week 0 DB	1 ^a	≤ 1
Week 4 DB	29	2 – 43
Week 8 DB	57	44 – 71 ^b
Week 26 OL	183	72 ^c – 190

Rx Day A = date of visit – date of first study drug injection in double-blind treatment period + 1

- a. Date of first study drug injection in double-blind treatment period.
- b. Rx Day 71 or the date of the first injection in OL period (if applicable), whichever comes first.
- c. For Week 26 OL, visit window was from Rx Day 72 or the date of the first injection in OL period + 1 (if applicable), whichever comes first, to Rx Day 190.

Vital signs and laboratory measurements will also be presented on the Any Adalimumab set using the visit windows in the following tables.

Table 6. Visit Windows for Analysis of CDAI and Vital Sign (Any Adalimumab)

Visit Week	Nominal Day	Time Window (Rx Day B Range)
Week 0	1 ^a	≤ 1
Week 2	15	2 – 22
Week 4	29	23 – 36
Week 6	43	37 – 50
Week 8	57	51 – 64
Week 10	71	65 – 78
Week 12	85	79 – 92
Week 14	99	93 – 106
Week 16	113	107 – 120
Week 18	127	121 – 134
Week 20	141	135 – 148

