Week 22	155	149 – 162
Week 24	169	163 – 176
Week 26	183	177 – 190

Rx Day B = date of visit – date of first dose of adalimumab + 1

- a. Date of first dose of adalimumab in double-blind treatment period.

Table 7. Visit Windows for Analysis of hs-CRP, Chemistry and Hematology (Any Adalimumab)

Visit Week	Nominal Day	Time Window (Rx Day B Range)
Week 0	1 ^a	≤ 1
Week 2	15	2 – 22
Week 4	29	23 – 36
Week 6	43	37 – 50
Week 8	57	51 – 71
Week 12	85	72 – 99
Week 16	113	100 – 127
Week 20	141	128 – 162
Week 26	183	163 – 190

Rx Day B = date of visit – date of first dose of adalimumab + 1

a. Date of first dose of adalimumab in double-blind treatment period.

Table 8. Visit Windows for Analysis of Urinalysis (Any Adalimumab)

Visit Week	Nominal Day	Time Window (Rx Day B Range)
Week 0	1 ^a	≤ 1
Week 4	29	2 – 43
Week 8	57	44 – 71
Week 12	85	72 – 112
Week 20	141	113 – 161
Week 26	183	162 – 190

Rx Day B = date of visit – date of first dose of adalimumab + 1

a. Date of first dose of adalimumab in double-blind treatment period.

Table 9. Visit Windows for Analysis of Fecal Calprotectin and IBDQ (Any Adalimumab)

Visit Week	Nominal Day	Time Window (Rx Day B Range)
Week 0	1 ^a	≤ 1
Week 4	29	2 – 43
Week 8	57	44 – 71
Week 26	183	72 – 190

Rx Day B = date of visit – date of first dose of adalimumab + 1

a. Date of first dose of adalimumab in double-blind treatment period.

Definition of Missing Data Imputation

The following imputation methods will be used to impute missing values in the efficacy analyses. In addition, an observed case analysis will be performed.

Non-Responder Imputation (NRI)

The NRI approach is used for binary efficacy variables. These variables can take values of 'Achieved' or 'Not Achieved' or may be missing for any reason including discontinuation from study. According to the NRI imputation approach, all missing value will be considered as 'Not Achieved.'

Subjects who dose-escalate from OL adalimumab 40 mg eow to OL adalimumab 80 mg eow due to disease flare or non-response will be imputed as 'Not Achieved' in the analysis of binary efficacy variables.

For the analysis of Week 26 efficacy variables only for dose-escalated subjects, the remission/response status will be determined based on the observed data at Week 26 after the dose escalation.

Last Observation Carried Forward (LOCF)

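### On the SAP's Rx Day B windows no on-schedule visit of a placebo-randomised subject reaches Week 24 or 26, so NRI as written caps the pooled descriptive Week 26 rate at about 50%

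*SAP*

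**What the plan says.** SAP 5.1 pools the arms: "The Any Adalimumab set consists of all enrolled subjects who received at least one injection of adalimumab". SAP 10.3 uses this set for the over-time analysis: "The analysis over time will also be performed for Any Adalimumab set (the entire study on or after the first dose of adalimumab"). These summaries are descriptive, with no between-group test. Four of the additional secondary endpoints are binary: remission, response, and each of these combined with an hs-CRP reduction.

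SAP 10.3 cites no window table for this analysis. SAP 6.0 does supply windows. Table 6 is titled "Visit Windows for Analysis of CDAI and Vital Sign (Any Adalimumab") and Table 7 "Visit Windows for Analysis of hs-CRP, Chemistry and Hematology (Any Adalimumab"). Both use the scale "Rx Day B = date of visit – date of first dose of adalimumab + 1".

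Two sentences in SAP 6.0 sit awkwardly with those titles. The lead-in to Tables 6 to 9 names no efficacy variable: "Vital signs and laboratory measurements will also be presented on the Any Adalimumab set using the visit windows in the following tables". The re-set of baseline is limited in the same way: "When analyzing laboratory parameters and vital signs on the Any Adalimumab analysis set, the Baseline Visit date is the date when" adalimumab is first given.

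Under SAP 4.2, subjects randomised to placebo receive placebo at Weeks 0 and 2 and "then will receive blinded adalimumab 160 mg at Week 4 and 80 mg at Week 6". The NRI rule in SAP 6.0 treats any missing binary value as not achieved, whatever the reason. It makes no exception for a window that a subject's schedule cannot reach.

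**The concern.** Counting days from the first adalimumab dose moves the placebo arm's whole schedule back by four weeks, while the window tables still run to Week 26. The last two CDAI windows therefore lie beyond the end of the study for half of the pooled set. If the empty cells are filled as non-response, the late part of the curve falls because of the calendar and not because of the drug. A reader comparing Week 16 with Week 26 could take that fall for loss of effect.

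The CDAI plus hs-CRP composites have a further difficulty. Tables 6 and 7 give different week labels to the same final visit, so its two components are not paired.

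**Working it through.** **Inputs.** Placebo arm's first adalimumab dose: study Week 4, nominal Day 29 (SAP 4.2, Table 2). Study Week 26: nominal Day 183 (Table 2). Visit allowance: ±3 days (SAP Table 1, note b). Arm size: 100 (SAP 4.3). Windows: Tables 6 and 7. Required CDAI visits: Weeks 2, 4, 6, 8, 12, 16, 20 and 26; Weeks 10, 14, 18, 22 and 24 are required only for onsite dosing (Protocol synopsis; SAP Table 1, note y).

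**The plan's own figures.** The SAP states no figure for these summaries. It supplies the 100 per arm, whose stated 90% power reproduces: full enumeration of the two-sided Fisher's exact test at 24% versus 47% gives 0.907.

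**Step 1: placebo-arm days.** Rx Day B = study day of visit − study day of first adalimumab dose + 1. The range takes both days to the ends of their allowances (dose on Day 26 to 32).

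| Required study visit | Rx Day B, nominal (range) | Table 6 CDAI window |
|---|---|---|
| Week 6 (Day 43) | 15 (9–21) | Week 2 (2–22) |
| Week 8 (Day 57) | 29 (23–35) | Week 4 (23–36) |
| Week 12 (Day 85) | 57 (51–63) | Week 8 (51–64) |
| Week 16 (Day 113) | 85 (79–91) | Week 12 (79–92) |
| Week 20 (Day 141) | 113 (107–119) | Week 16 (107–120) |
| Week 26 (Day 183) | 155 (149–161) | Week 22 (149–162) |

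Last row: 183 − 29 + 1 = 155; 180 − 32 + 1 = 149; 186 − 26 + 1 = 161. The Week 24 window opens at 163 and the Week 26 window at 177. Even after the earliest allowed dose (Day 26), these need a visit on study Day 188 (163 + 25) or Day 202 (177 + 25). The last on-schedule visit is Day 186.

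**Step 2: composites.** hs-CRP from the same final visit (149–161) falls in the Table 7 Week 20 window (128–162), while its CDAI is labelled Week 22. Table 7 has no Week 22 row. An onsite doser's study Week 24 CDAI (169 − 29 + 1 = 141; range 135–147) is labelled Week 20, so it would be matched with hs-CRP taken at study Week 26.

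**Step 3: ceiling on the pooled Week 26 NRI rate.** Let k be the number of placebo subjects who never receive adalimumab and so are outside the set. Ceiling = 100 / (200 − k). The values of k above 0 are assumptions; the documents give none.

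- k = 0: 50.0%
- k = 5: 51.3%
- k = 10: 52.6%
- k = 15: 54.1%

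**Step 4: reported against true rate.** Let pA and pP be the arms' true rates at that time point. With equal arms, reported = pA/2, true pooled = (pA + pP)/2, and the ratio is pA/(pA + pP). With assumed rates:

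| pA | pP | Reported | True pooled | Ratio |
|---|---|---|---|---|
| 50% | 40% | 25% | 45% | 0.56 |
| 50% | 50% | 25% | 50% | 0.50 |
| 50% | 60% | 25% | 55% | 0.45 |

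If both arms held a constant 50% with complete data, the pooled curve would read 50% at Week 16 and 25% at Week 26.

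**The case against.** The best defence is that the harm needs the most literal reading of NRI. SAP 10.3 confines this analysis to the study period from the first adalimumab dose, so a time point after a subject's study has ended could be called not evaluated rather than missing. The NRI sentence in SAP 10.3 also follows directly on endpoints compared between groups or with a constant, and these summaries are neither. That is a sensible reading, and a programmer might adopt it. But the general NRI rule in SAP 6.0 covers binary efficacy variables without such a limit, and no text gives the exception. The denominator should not be left to be settled at programming.

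It is also fair that the ceiling is reached only if every adalimumab-arm subject is in remission; the ratio in Step 4 says more, and it rests on assumed rates. Observed-case and LOCF results are planned as well, and they are not distorted in this way.

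Three stronger readings are tempting and are not supported:

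- *That the SAP gives no day scale.* Tables 6 and 7 do give one, and name CDAI and hs-CRP. What is missing is a citation in SAP 10.3 and a lead-in consistent with the table titles. Because of that lead-in, a reader might infer that windows counted from first study drug (Table 2) apply; the Week 24 and 26 gap would then not arise.
- *That every placebo-randomised subject must fail.* This holds for on-schedule visits. A dose on Day 26 and a late visit on Days 188 to 190 give Rx Day B 163 to 165, inside the Week 24 window. An unscheduled visit could do the same.
- *That the main results are biased.* The Week 4 primary comparison precedes any adalimumab in the placebo arm. The Week 26 responder endpoint uses the ITT set as its primary population, with Table 2 windows counted from first study drug.

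**Conclusion.** The point stands as a minor one. With the Table 6 and 7 windows and NRI as written, on-schedule placebo-randomised subjects count as non-responders at Weeks 24 and 26 by design. The pooled Week 26 NRI rate is then capped at 50% with 100 per arm, and is about half the true rate if the arms are alike. This rests on three assumptions: Rx Day B is the intended scale, visits keep to the ±3-day allowance, and arms are of equal size.

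The scope is the descriptive NRI summaries of four additional secondary endpoints. No hypothesis test changes. Home dosing also leaves CDAI values missing at the optional visits, in both arms, but the documents do not give the share dosing at home, so no size is put on that. A late fall in the NRI curve might be read as loss of effect; under these rules it could arise from the schedule alone.

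**What to change.** In SAP 10.3:

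- Cite Tables 6 and 7 as the windows for the Any Adalimumab over-time efficacy summaries, and bring the lead-in to those tables into line. If the sponsor intended days from first study drug, say that instead.
- Limit the NRI denominator at each time point to subjects whose randomised arm has a required visit in that window: Weeks 2, 4, 6, 8, 12, 16, 20 and 26 for the adalimumab arm; Weeks 2, 4, 8, 12, 16 and 22 for the placebo arm. Keep early discontinuers as failures at those visits.
- Show n and results by randomised arm.
- Build each CDAI plus hs-CRP composite from the same study visit, and report it under that visit's CDAI window label, because Table 7 has no Week 22 row.

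The cost is SAP wording and programming, with no new data. The drawback is that denominators vary: Weeks 6, 20, 22 and 26 rest on one arm, so successive points do not describe the same subjects. Showing the arms separately makes this visible. Ending the pooled display at Week 22 would be simpler, but would drop the adalimumab arm's Week 26 result.
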